4.1. General Considerations

Statistical analysis of this study will be the responsibility of Eli Lilly and Company (Lilly) or its designee. Some analyses and summaries described in this analysis plan may not be conducted if not warranted by data (for example, too few events to justify conducting an analysis). Additional exploratory analyses of the data may be conducted as deemed appropriate.

Unless otherwise noted, all tests of treatment effects will be conducted at a 2-sided alpha level of 0.05, and confidence intervals (CIs) will be calculated at 95%, 2-sided. All tests of interactions between treatment groups and other factors will be conducted at a 2-sided alpha level of 0.10.

Unless stated otherwise, statistical summaries and analyses will be conducted based on the planned randomized treatment groups: placebo, LY 100 mg, LY 400 mg, and LY 800 mg.

The primary estimand (a precise definition of the treatment effect to be estimated) of interest in comparing the efficacy of LY3561774 doses with placebo is the efficacy estimand (Section 1.1). The primary efficacy assessment, guided by the efficacy estimand, will be conducted using the efficacy analysis set (EAS) (Section 3). Subjects who received only the first dose of LY3561774 will be considered "on-treatment" during Day 1 to Day 90, whereas subjects who received both doses will be considered "on-treatment" during the entire treatment and assessment period.

Unless otherwise specified, safety assessments will be guided by an estimand comparing the safety of LY3561774 doses with placebo, irrespective of adherence to the study intervention. Thus, safety analyses will be conducted using the safety analysis set (SAS) (Section 3).

For continuous measures, summary statistics will include sample size, mean, standard deviation (SD), median, minimum, and maximum for both the actual and the change from baseline measurements. Least squares (LS) means and standard errors derived from the analysis models, mixed model repeated measures (MMRM) and analysis of covariance (ANCOVA) will also be displayed for the change from baseline measurements. Treatment comparisons will be displayed showing LS means and 95% CIs for treatment differences, along with p-values for treatment comparisons. For categorical measures, summary statistics will include sample size, frequency, and percentages. A logistic regression model will be used to examine the treatment difference in binary efficacy outcomes with missing endpoints imputed. Fisher's exact test or Pearson's chi-square test will be used for treatment comparisons in other categorical outcomes.

For analyses of efficacy parameters involving an ANCOVA model, missing data will be imputed using the multiple imputation method under the missing at random assumption. Such an approach is valid when the propensity for a data point to be missing is not related to the missing data, but is related to some of the observed data. Estimates and standard errors from multiple imputed datasets will be combined using Rubin's rules.

Endpoints that compare treatment groups based on percent change from baseline will be conducted by log-transformation of the dependent variables. Standard errors and 95% CIs will be constructed using the delta method. The LS means and standard error for each treatment, difference in LS means between arms, and corresponding 95% CIs will be calculated as shown in Table EZCB.4.1, where Z_b is the baseline of the log of the response.

Table EZCB.4.1 Summary of Reported Quantities for Variables Requiring Log-Transformation

Qua	nntity	Change from Baseline	Percent Change from Baseline
Within	Estimate	$\left[\exp\left(\hat{\mu}_{\Delta Z,k} ight) - 1 ight]\exp(ar{Z}_{b\cdot})$	$\left[\exp\left(\hat{\mu}_{\Delta Z,k}\right)-1\right] imes 100$
Treatment	SE	$\exp(\overline{Z}_{b.})\exp(\hat{\mu}_{\Delta Z,k})\cdot\widehat{SE}_{\Delta Z,k}$	$\exp(\hat{\mu}_{\Delta Z,k}) \cdot \widehat{SE}_{\Delta Z,k} \times 100$
	P-value	NR	p_k
Between- Treatment Difference	Estimate	$[\exp(\hat{\mu}_{\Delta Z,k}) - \exp(\hat{\mu}_{\Delta Z,R})] \cdot \exp(\bar{Z}_b)$	$(\exp(\hat{\mu}_{\Delta Z,k\ vs\ R})-1)\times 100$
(Treatmen t k vs. Reference Arm)	SE	$e^{\bar{Z}_{b}} \sqrt{e^{2\hat{\mu}_{\Delta Z,k}} \cdot \left(\widehat{SE}_{\Delta Z,k}\right)^2 + e^{2\hat{\mu}_{\Delta Z,R}} \cdot \left(\widehat{SE}_{\Delta Z,R}\right)}$	$\exp(\hat{\mu}_{\Delta Z, k \ vs \ R}) \cdot \widehat{SE}_{\Delta Z, k \ vs \ R} \times 100$
12)	P-value	NR	P∆Z,k vs R
	95% CI	Estimate $\pm \Phi^{-1} (1 - \frac{\alpha}{2}) * SE$	$(\left[\exp\left(L_{\Delta Z,k\ vs\ R}\right)-1\right]\times 100, \left[\exp\left(U_{\Delta Z,k\ vs\ R}\right)-1\right]\times 100)$

Abbreviation: CI = confidence interval; NR = not reported; SE = standard error.

In general, a time-averaged parameter will refer to the area under the curve (AUC) constructed using the trapezoidal rule, applied to the parameter according to the scheduled time, divided by the length of observation. For example, a time-averaged dependent variable for Days 30 to 180 will equal AUC/150, where AUC represents the AUC constructed by the trapezoidal rule.

Unless otherwise specified, baseline is defined as the last non-missing measurement recorded on or before the randomization visit, prior to first dose of intervention.

When considering treatment-emergent abnormal safety laboratory values and vital signs, baseline observation will start from the screening visit and end prior to, or at, the randomization visit, wherein all scheduled and unscheduled measurements will be included. The baseline for the treatment-emergent safety analysis will be the maximum/minimum from all measurements taken during the baseline period. For postbaseline measurements, all scheduled and unscheduled measurements in the analysis period will be included. The maximum/minimum from all measurements taken during the analysis period will be used in the treatment-emergent safety analysis. The end of Study EZCB participation for a participant will be the earliest of date of death, the date of withdrawal from further participation in the study, or the date of the safety follow-up visit (Visit 801). For participants considered to be lost to follow-up, end of Study EZCB participation will be the date participant is lost to follow-up as reported by the investigator. Participant data included in the database after the last date of Study EZCB participation (including the safety follow-up period) will be excluded from statistical analysis.

Statistical treatment comparisons will only be performed between LY3561774 doses and placebo. Since the trial is not adequately powered to detect differences among LY3561774 doses, comparisons across LY3561774 doses will not be performed unless otherwise specified. Not all analyses described in this SAP will necessarily be included in the clinical study reports. Any analysis described in this SAP and not provided in the clinical study reports will be available upon request.

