1.2. Study Design

Study EZCB is a Phase 2, randomized, double-blind, placebo-controlled, parallel-arm study to investigate the efficacy and safety of LY3561774 in adults with mixed dyslipidemia.

Participants will be randomly assigned in a 2:1:2:2 ratio to placebo: LY3561774 100 mg:400 mg:800 mg. Placebo participants will be randomly assigned such that each dose cohort will have a matching placebo cohort that receives the same dose volume to maintain the study blind.

Participants will be stratified according to the Visit 1 TG level of less than 250 mg/dL and 250 mg/dL or greater.

Study intervention administration is by subcutaneous injection. Dosing will occur twice during the study, on Day 0 and Day 90 ± 5 days.

If a participant's ApoB levels do not return to 80% of baseline or higher on Day 270, then the participant will continue to the follow-up visit at Day 360.

If a participant's ApoB levels return to ≥80% of baseline or higher on Day 270, then Day 270 is the participant's last study visit.

Figure EZCB.1.1 illustrates the study schema.

2. Statistical Hypotheses

The Study EZCB hypothesis for the primary objective is that at least one dose of LY3561774 100 mg, 400 mg, or 800 mg is superior in percent change from baseline for ApoB relative to placebo at Day 180 in participants with mixed dyslipidemia.

Thus, the null hypothesis to be tested in relation to the primary estimand is that LY3561774 100 mg, 400 mg and 800 mg are not different from placebo with respect to percent change in ApoB from baseline to Day 180.

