4.3.2. Main Analytical Approach

Mean percent change of ApoB will be analyzed using the MMRM model for the efficacy estimand. As described in Section 4.1, the response variable will be log-transformed.

A restricted maximum likelihood-based MMRM analysis will be used to analyze continuous longitudinal variables. All longitudinal observations taken at each scheduled postbaseline visit will be included in the analysis. The model for the analysis of the primary efficacy endpoint of percent change from baseline in ApoB will include the fixed class effects of treatment group (placebo, LY3561774 100 mg, LY3561774 400 mg, and LY3561774 800 mg), visit, treatment-by-visit interaction, Visit 1 TG stratum (lower than 250 mg/dL, 250 mg/dL or greater) as well as the continuous baseline value of the log-transformed dependent variable.

An unstructured covariance structure will be used to model the within-participant errors. Significance tests will be based on LS means and type III tests. If this analysis fails to converge, these covariance structures will be tested in order

- Toeplitz with heterogeneity
- autoregressive with heterogeneity
- compound symmetry with heterogeneous variances
- Toeplitz
- · autoregressive, and
- compound symmetry without heterogeneous variances.

The first covariance structure that converges will be used. The Kenward-Roger approximation will be used to estimate denominator degrees of freedom.

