4.5.2. Analyses using the Full Analysis Set

These two exploratory study objectives will be analyzed using the full analysis set (FAS) and the associated treatment-regimen estimand.

Absolute change from baseline at Day 180 for

- non-HDL-C
- LDL-C
- HDL-C
- ApoB, and
- TG.

Percent change from baseline at Day 180 for

- non-HDL-C
- LDL-C
- HDL-C
- · ApoB, and
- TG.

Missing data for the dependent variables at each time point will be imputed using multiple imputation as detailed in Section 4.1.

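### The between-treatment SE for absolute change in SAP Table EZCB.4.1 omits the covariance of the two LS means, so some exploratory intervals are too wide if uneven TG strata are weighted equally

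*SAP*

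**What the plan says.** SAP 4.1 log-transforms the dependent variable for endpoints compared on percent change, states that "Standard errors and 95% CIs will be constructed using the delta method", and refers to Table EZCB.4.1 for the quantities to report.

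- **Absolute change, between-treatment SE.** Up to the point where the cell breaks off, the formula reads "e^{\bar{Z}_{b}} \sqrt{e^{2\hat{\mu}_{\Delta Z,k}} \cdot \left(\widehat{SE}_{\Delta Z,k}\right)^2 + e^{2\hat{\mu}_{\Delta Z,R}} \cdot \left(\widehat{SE}_{\Delta Z,R". It has one term for arm k, one for reference arm R, and no cross term.
- **Percent change, between-treatment SE.** The formula is "\exp(\hat{\mu}_{\Delta Z, k \ vs \ R}) \cdot \widehat{SE}_{\Delta Z, k \ vs \ R} \times 100". The SE here is that of the model contrast between k and R.
- **Absolute-change interval.** It is "Estimate $\pm \Phi^{-1} (1 - \frac{\alpha}{2}) * SE". The p-value in that column is marked as not reported.

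The model in SAP 4.3.2 contains treatment and "visit, treatment-by-visit interaction, Visit 1 TG stratum (lower than 250 mg/dL, 250 mg/dL or greater) as well as the continuous baseline value" of the log-transformed variable. The stratum effect and the baseline slope are therefore common to all four arms. The section adds "Significance tests will be based on LS means and type III tests" but does not say how LS means weight the strata. On the strata, SAP 1.2 says "Participants will be stratified according to the Visit 1 TG level of less than 250 mg/dL and 250 mg/dL or greater".

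SAP 4.5.2 lists "Absolute change from baseline at Day 180 for" five lipid measures, analysed in the full analysis set with multiple imputation. It names no model terms. SAP 4.5 sends exploratory analyses to the general methods of 4.1.

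**The concern.** The table names the delta method, but for absolute change it gives a formula that is the delta-method SE only when the two LS means are uncorrelated. In a model with shared coefficients they need not be. If they are positively correlated, the formula overstates the SE of the difference and the interval is too wide.

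That column reports no p-value, so the interval is its only inferential output. At stake is the width of the intervals for absolute change in ApoB, LDL-C, HDL-C, non-HDL-C and TG at Day 180, and for any other log-transformed measure reported as change.

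**Working it through.** **The plan's own figure.** The SAP gives no numerical SE for absolute change. The nearest figure that can be reproduced is the power statement in SAP 5. Completers are 175 x 2/7 x 0.8 = 40 and 175 x 1/7 x 0.8 = 20 (the 20% dropout is in Protocol 9.5). With SD 15 and difference 30:

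- 40 v 40: 30 / (15 x sqrt(1/40 + 1/40)) = 8.94.
- 20 v 40: 30 / (15 x sqrt(1/20 + 1/40)) = 7.30.

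Both give power above 99.99%, which agrees with the stated figure of more than 99%.

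**Formulas.** Let a = exp(mu_k) and b = exp(mu_R), and let V_k, V_R and C be the variances and covariance of the LS means. The common factor exp(Zb) cancels from the ratio. The placebo SE is read as squared.

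- Table: SE = sqrt(a²V_k + b²V_R)
- Delta method: SE = sqrt(a²V_k + b²V_R - 2abC)

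**Where C comes from.** Suppose a share p of every arm is in one stratum, and N participants in total. With equal stratum weights, each LS mean is the arm's raw mean plus a multiple of the estimated stratum effect. That multiple has size |0.5 - p| and is the same in every arm. Hence C = (0.5 - p)² x sigma² / (N p (1 - p)) and V_k = sigma²/n_k + C. C is zero at p = 0.5 and positive otherwise.

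**Inputs.** Arms are 40/20/40/40, so N = 140. For 800 mg, a/b = 0.70, matching the planned -30%. For 100 mg, a/b = 0.85 is an assumption. The split is an assumed range. Sigma cancels.

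**Example, 800 mg at 80/20, in units of sigma².**

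- C = 0.09 / (140 x 0.16) = 0.00402
- V = 1/40 + 0.00402 = 0.02902
- Table variance = (0.49 + 1) x 0.02902 = 0.04324
- Full variance = 0.04324 - 2 x 0.70 x 0.00402 = 0.03761
- Ratio of SEs = sqrt(0.04324 / 0.03761) = 1.072

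**Table SE divided by full SE**

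| Split | 800 mg, ANCOVA | 100 mg, ANCOVA | 800 mg, MMRM | Coverage of nominal 95% CI (800 mg, ANCOVA) |
|---|---|---|---|---|
| 50/50 | 1.000 | 1.000 | 1.000 | 95.0% |
| 60/40 | 1.006 | 1.004 | 1.002-1.005 | 95.1% |
| 70/30 | 1.025 | 1.019 | 1.009-1.021 | 95.6% |
| 80/20 | 1.072 | 1.054 | 1.03-1.06 | 96.4% |
| 90/10 | 1.210 | 1.163 | 1.08-1.18 | 98.2% |

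The MMRM column assumes ten post-baseline visits and a within-participant correlation of 0.3 to 0.8. A simulation of 4,000 trials per split, with a baseline covariate and log-scale SD 0.2, gave mean ANCOVA ratios for 800 mg of 0.999, 1.005, 1.025, 1.072 and 1.210. At 90/10 it gave coverage of 98.3% with the table SE and 95.2% with the covariance included.

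**When the effect vanishes.** With observed-margin weights the multiple of the stratum effect is zero, so the ratio is 1.000 at every split. Without the stratum in the model, only chance baseline imbalance is left, which moves the ratio by less than 1% either way.

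**Net of the normal quantile.** On 134 df the t quantile is 1.009 times the normal one. Relative to a t interval with the full SE, the ANCOVA width for 800 mg is 1.006/1.009 = 0.997 at 60/40, 1.025/1.009 = 1.016 at 70/30 and 1.072/1.009 = 1.06 at 80/20. Under MMRM at 70/30 it is about 1.00 to 1.01.

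**The case against.** The strongest objection is to the evidence. The formula cell is damaged at its right-hand end in the available text, where the placebo SE has lost its square. A covariance term could have stood there too. The text alone cannot settle this, so the source table must be checked before anything is changed. For the same reason, a reader might infer that the plan forgets the square, which taken literally makes the 800 mg SE more than four times too large at log SD 0.2. That is probably an extraction fault and is not claimed here.

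The sentence naming the delta method is not wrong. Applied properly, the method includes the covariance. Any fault lies in the table's formula.

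The conditions are also not given. No LS-mean weighting is stated, and equal weights are only the conventional reading. SAP 4.5.2 lists no ANCOVA terms. The one ANCOVA whose adjustment the Protocol describes (9.3.4, for AUC) names baseline ApoB and no TG stratum. The log-transformation sentence in SAP 4.1 concerns percent-change endpoints, and 4.5.2 does not say that it uses the absolute-change column, although SAP 4.5 points to 4.1 and the table provides that column. No TG split is given. The eligible range is 150 to 499 mg/dL with the cut at 250 (Protocol 5.1 and 6.3), and nothing in the design holds the strata even, but that does not tell us the split. These points make the effect conditional. They do not make the formula right for correlated LS means.

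A reader might infer that the intervals are too wide whenever the strata are unequal. The working does not support that: at 60/40 the normal quantile more than cancels the inflation. A reader might also infer that the absolute and percent-change intervals should agree. They should not, because one is a difference on the measurement scale with a symmetric interval and the other is a back-transformed ratio with an asymmetric one.

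**Conclusion.** The point holds as a minor, conditional error. As the table reads, its SE for absolute change is not the delta-method SE when the LS means are correlated. If the TG stratum is in the model and LS means weight strata equally, the SE for 800 mg under ANCOVA is too large by about 0.6% at 60/40, 2.5% at 70/30 and 7% at 80/20. Under MMRM it is too large by less. There is no error at 50/50 or with observed-margin weights, and no systematic error without the stratum term. After the offset of about 0.9% from the normal quantile, the interval is materially too wide only at splits more uneven than about 70/30.

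The splits are assumptions, and the error is conservative. It reaches only the exploratory absolute-change intervals and any log-transformed measure reported as change. A reader might infer that the ApoB result is in doubt. It is not: the primary and secondary percent-change comparisons use the contrast SE, and no p-value comes from the affected column.

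**What to change.** 1. Check the absolute-change SE cell against the source of Table EZCB.4.1, both for the square on the placebo SE and for any term lost at the right-hand end.
2. If the covariance is absent there, replace the formula by SE = exp(Zb) x sqrt(exp(2 mu_k) SE_k² + exp(2 mu_R) SE_R² - 2 exp(mu_k + mu_R) Cov(mu_k, mu_R)), with Cov taken from the model's LS-mean covariance matrix.
3. Where multiple imputation is used, compute this SE within each imputed dataset before applying Rubin's rules.
4. State in SAP 4.1 or 4.3.2 how LS means weight the TG strata, and list the ANCOVA terms for the analyses in 4.5.2.

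The cost is one formula, two clarifying statements and a small code change. No data collection, sample size or test is affected.

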4.2. Participant Dispositions

A listing and summary of Study EZCB participant disposition for all randomly assigned participants will be provided at the primary and final database locks, respectively. Frequency counts and percentages of all participants screened, randomly assigned, and receiving at least 1 dose of study drug will be presented by treatment groups. A listing and summary of randomly assigned participants not receiving the study drug will be provided. All participants who discontinue Study EZCB and/or the study drug will be identified, and the extent of their participation in Study EZCB will be reported. If known, a reason for their discontinuation will be given. The primary reasons for discontinuation will be listed and summarized by treatment groups.

Details about participant dispositions are included in the appendices: the demographic and baseline characteristics (Appendix 1, Section 6.1), historical illnesses and preexisting conditions (Appendix 2, Section 6.2), treatment compliance (Appendix 3, Section 6.3), concomitant medications (Appendix 4, Section 6.4), and important protocol deviations (Appendix 5, Section 6.5).

4.3. Primary Endpoint Analysis

The primary efficacy assessment, guided by the efficacy estimand, will be conducted using the efficacy analysis set (EAS) for the primary endpoint (percent change from baseline at Day 180 for ApoB).

The hypothetical strategy defined relative to the efficacy estimand – had participants adhered to the randomized treatment – will be used to handle the intercurrent events of permanent discontinuation of intervention, initiation of excluded medications taken during the study, and new initiation of any lipid-lowering drug required to be on a stable regimen prior to treatment per the protocol inclusion criteria. Only data collected before the occurrence of any intercurrent events will be used in the MMRM analysis. The MMRM analysis will then implicitly impute the potential efficacy measures (after the intercurrent events) if participants had not had intercurrent events.

See Section 10.7.3 of the Study EZCB protocol for a list of prohibited concomitant medications. Excluded medication and lipid lowering drugs are listed in Table EZCB.4.2.

Table EZCB.4.2 List of Medications

Prohibited Concomitant Medications and Procedures for Study EZCB			
Drug Class/Procedure	Comments		
Lipid lowering therapy including, but not limited to triglyceride-lowering medication example: Vascepa® (icosapent ethyl)	Prohibited within 4 weeks prior to screening and during the study.		
simvastatin 80 mg per dayfibratesbile acid sequestrants	Prohibited within 6 weeks prior to screening and during the study.		
over-the-counter and health food preparations o examples: red yeast rice, fish oil, omega-3 fatty acid >100 mg/day niacin >250 to <1000 mg/day or other nicotinic acid derivatives probucol	Prohibited within 8 weeks prior to screening and during the study.		
• niacin >1000 mg per day	Prohibited within 16 weeks prior to screening and during the study.		
inclisiran or any other small interfering ribonucleic acid	Prohibited within 12 months prior to screening and during the study.		
Warfarin or other coumarins	Prohibited within 1 month prior to screening and during the study.		
Direct thrombin inhibitors	Prohibited within 1 month prior to screening and during the study.		
Factor Xa inhibitors	Prohibited within 1 month prior to screening and during the study.		
Heparins or heparinoids	Prohibited within 1 month prior to screening and during the study.		
Systemic corticosteroids, cyclosporine, isotretinoin, or anabolic agents Exceptions: local, topical, intra-articular, inhalation, or nasal corticosteroids	Prohibited within 3 months prior to screening and during the study.		
Anti-sense oligonucleotides Exception: mRNA vaccines	Prohibited within 6 months prior to screening and during the study.		
Tamoxifen	Prohibited.		
HIV protease inhibitors, cyclophosphamide or systemic retinoids	Prohibited.		
Medications associated with weight gain or loss Exception: if participant is on a stable dose for at least 3 months prior to screening and will continue taking a stable dose during the study.	Prohibited.		

